Effect of FMT on antibiotic-associated microbial diversity and function collapse¹²:

Since the trial above had antibiotics followed by FMT, we could study the impact of antibiotics on the microbial function (bile acid metabolism, short-chain fatty acid production) and microbiota diversity. There was a collapse of microbial diversity post-antibiotics that recovered after the FMT. In addition, after antibiotics, there was a reduction in deconjugation, desulfation and conversion of primary to secondary bile acids in the stool. These were reversed with FMT. Most importantly, the collapse in beneficial short-chain fatty acid production was reversed by one FMT in this population.

Experience with oral FMT in *C. difficile* and in cirrhosis:

In studies of capsules and nasojejunal/nasogastric infusion of the fecal contents in *C. difficile*, there was an excellent safety profile without serious adverse events

(Youngster et al JAMA 2014, Youngster et al Clin Infect Dis 2014). A pooled analysis of data from trials comparing oral vs. colonoscopic administration showed that both routes were safe and effective for C. difficile (Postigo et al Infection 2012).

There has been one study in the literature of nasojejunal infusion of fecal transplant from several donors in patients with severe alcoholic hepatitis, most of whom have cirrhosis. This case series also demonstrated a good safety profile and was able to show a survival benefit compared to historical controls (Phillips et al Clin Gastroenterol Hep 2016).

The team's experience with FMT in cirrhosis using capsules:

Fecal transplant using the oral capsule route is safe: In a current ongoing safety trial, which is powered for 20 individuals (10 in placebo and 10 with FMT capsules using a rational donor) under FDA IND, we have currently enrolled all 20 patients (10 in placebo and 10 to FMT)¹¹. All 10 FMT patients have tolerated the procedures and do not have any safety signal compared to the ones in placebo group. They have all safely undergone safety capsule testing, swallowed all the oral capsules required for placebo or FMT without any issues¹¹. This study is being performed under an approved FDA IND 17239 and is a phase I study of capsules. There is good background information that this will be safe and well-tolerated, but we will aggressively monitor every patient as outlined below.

Concentration of bacteria in capsules and enemas in the oral and enema preparations used for the studies above:

		Mean	St Dev

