Aerobes	Fresh	2.53E+05	1.76E+05
	1 freeze-thaw	4.30E+05	4.43E+05
Anaerobes	Fresh	5.80E+07	3.96E+07
	1 freeze-thaw	6.20E+07	5.29E+06

CFUs per mL of Capsules G3 Microbial Emulsion Matrix

_CFUs per mL of stool homogenized 1:1 (w/v) with buffer containing 12.5% glycerol and 0.9% saline, after one freeze-thaw cycle

	per mL
Aerobes	4.53E+06
Anaerobes	1.47E+09
Spores	2.00E+06

These concentrations will be used for the upcoming trial to ensure that the material concentrations in our older trials are expanded.

- We anticipate providing 5 capsules at a time for the oral FMT and 60ml of the FMT enema.
- The placebo for the oral FMT will be made using identical capsules as the active drug, except it will contain 10%/weight trehalose (the cryoprotectant used in preparation of freeze-dried microbiota) and the rest carboxymethylcellulose. Since the capsules are not transparent and have no specific smell or taste, there should be no difficulty in maintaining double blinding.
- The placebo for the liquid formulation is non-bacteriostatic, sterile phosphate buffered saline containing 10% USP grade glycerol. Each dose will be packaged in individual cryobags, just as the active drug.

Study Design

Overall objective: To determine the effect of dual oral and rectal administration of FMT from a rational donor on clinical outcomes (hospitalizations, brain function, quality of life) and host-microbiota interactions (microbial composition and bile acid composition with systemic and intestinal inflammation), compared to single route of administration and placebo, along with a second oral capsular FMT vs placebo administration in patients with cirrhosis and HE using a randomized, phase II clinical trial.

Design overview:

Four groups of outpatients with cirrhosis will be randomized using random sequence generator into placebo and FMT groups and followed for 6 months under an FDA IND double-blind clinical trial.

Group 1: Dual oral and rectal FMT, Group 2: Oral FMT and rectal placebo, Group 3: Oral placebo and rectal FMT and Group 4: Oral and rectal placebo

A repeat oral capsular FMT vs placebo based on the group assignments above will be provided to every subject in at day 30.

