- G. Hospitalization for any non-elective cause within the last 1 month
- H. Patients who are aged >75 years
- I. Patients who are pregnant or nursing (will be checked using a urine pregnancy test)
- J. Patients who are incarcerated
- K. Patients who are incapable of giving their own informed consent

- L. Patients who are immuno-compromised due to the following reasons:
 - a. HIV infection (any CD4 count)
 - b. Inherited/primary immune disorders
 - c. Current or recent (<3 mos) treatment with anti-neoplastic agent
 - d. Current or recent (<3 mos) treatment with any immunosuppressant medications [including but not limited to monoclonal antibodies to B and T cells, anti-TNF agents, glucocorticoids, antimetabolites (azathioprine, 6-mercaptopurine), calcineurin inhibitors (tacrolimus, cyclosporine), mycophenolate mofetil]. Subjects who are otherwise immunocompetent and have discontinued any immunosuppressant medications 3 or more months prior to enrollment may be eligible to enroll.
- M. Patients on renal replacement therapy
- N. Patients with untreated, in-situ colorectal cancer
- O. Patients with a history of chronic intrinsic GI diseases such as inflammatory bowel disease (ulcerative colitis, Crohn's disease or microscopic colitis), eosinophilic gastroenteritis or celiac disease
- P. Major gastro-intestinal or intra-abdominal surgery in the last three months
- Q. Patients who have received FMT within last 6 months

Other Exclusion Criteria:

Enema-related

- (1) Platelet count<25,000
- (2) Grade IV hemorrhoids

Safety-related:

- (1) Dysphagia
- (2) History of aspiration, gastroparesis, intestinal obstruction
- (3) Ongoing antibiotic use (except for Rifaximin)
- (4) Severe anaphylactic food allergy
- (5) Allergy to ingredients Generally Recognized As Safe in the FMT capsules (glycerol, sodium chloride, hypromellose, gellan gum, titanium dioxide, theobroma oil)
- (6) Adverse event attributable to prior FMT
- (7) ASA Class IV or V
- (8) Pregnant or nursing patients
- (9) Acute illness or fever within 48 hours of the day of planned FMT
- (10) Immunocompromised due to medical conditions
- (11) Probiotics use within the last 48 hours of the day of planned FMT
- (12) Any condition that the physician investigators deem unsafe, including other conditions or medications that the investigator determines puts the participant at greater risk from FMT

Intervention

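### The capsule-allergy exclusion names neither ingredient of the oral placebo fill, and the protocol does not state the formulation of the active capsule

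*Combined protocol and SAP*

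**What the plan says.** Under Other Exclusion Criteria, Safety-related item (5) excludes "Allergy to ingredients Generally Recognized As Safe in the FMT capsules" and gives six in parentheses: "glycerol, sodium chloride, hypromellose, gellan gum, titanium dioxide, theobroma oil". Placebo capsules are not mentioned.

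The bullets just before Study Design describe the oral placebo. On the shell: "The placebo for the oral FMT will be made using identical capsules as the active drug". On the fill: "it will contain 10%/weight trehalose (the cryoprotectant used in preparation of freeze-dried microbiota) and the rest carboxymethylcellulose".

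The bacterial counts appear just above those bullets. Their heading is "Concentration of bacteria in capsules and enemas in the oral and enema preparations used for the studies above", so they come from the earlier trials. The capsule table is captioned "CFUs per mL of Capsules G3 Microbial Emulsion Matrix". The text then says "These concentrations will be used for the upcoming trial". The background section reports that the team has moved from an earlier supplier to the University of Minnesota facility.

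The Dosage entry under Intervention gives the oral dose as five capsules, active or placebo, at baseline and again at day 30. Preparation and handling of FMT material describes frozen storage and thawing of capsules. No section gives the full composition or the fill volume of the active capsule.

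**The concern.** An excipient-allergy exclusion protects patients only if its list matches what they will swallow. Here the one capsule fill that the protocol spells out shares no ingredient with the list, and the criterion is worded for the active capsules only. A site that follows the text would not be led to ask about either placebo fill ingredient.

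Both the patient and the safety comparison are at stake. The section on specific issues to be captured says that FMT safety findings will be judged against the placebo groups. An avoidable excipient reaction in a placebo arm would therefore also blur that comparison.

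A second, smaller question comes from the same page. The placebo text mentions freeze-dried microbiota, while the counts carried into this trial are for an emulsion. The reader cannot tell which product the counts describe.

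**Working it through.** No plan figure needs reproducing. The check is a comparison of texts with a few counts.

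**1. Allergy list against the stated placebo fill**

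| Ingredient of oral placebo fill | In exclusion (5)? | In any other eligibility criterion? |
|---|---|---|
| Trehalose | No | No |
| Carboxymethylcellulose | No | No |

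The list has six ingredients and the placebo fill has two. The overlap is 0 of 2. Because the two capsules are said to be identical apart from their contents, some listed items may belong to a shared shell. That would not bring either fill ingredient onto the list.

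**2. Who is assigned the placebo fill**

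The Sample size paragraph plans 25 patients in each of four groups. Groups 3 and 4 receive oral placebo: 2 × 25 = 50 of 100. Each is assigned 5 capsules at baseline and 5 at day 30, so 5 + 5 = 10 capsules if both doses are taken. Visit 4 lets some patients miss the second dose: refusal, transplant, death or hospice, an FMT-related infection or SAE, or current antibiotic treatment. The figure of 50 is therefore planned exposure at baseline and an upper limit at day 30.

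**3. Whether screening can allow for the arm**

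Eligibility is assessed at Visit 1 before randomisation and re-confirmed at Visit 2, in a double-blind trial. The screener does not know which capsule the patient will get, so a list written for one capsule does not cover both.

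**4. Whether another safeguard closes the gap**

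- Safety-related (4) covers only severe anaphylactic food allergy.
- Safety-related (12) leaves unsafe conditions to the investigator's judgement and names no excipient.
- The test capsule at Visit 1 checks swallowing.
- Allergic reaction is listed among foreseeable risks and among issues to be captured. The mitigation offered under Protection against risk is a single donor plus the adverse event chart. Donor choice does not bear on excipients.
- Neither the solicited adverse event list nor the Adverse Event Grading Chart has an allergy entry.

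Exclusion (5) is thus the only control aimed at capsule excipients.

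**5. Capsule counts**

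After one freeze-thaw, the capsule table gives a mean of 6.20E+07 anaerobic CFU per mL. For a fill volume of V mL, five capsules hold 5 × V × 6.20E+07 = 3.10E+08 × V. The protocol does not give V, so the product cannot be evaluated. If the second table describes the enema material, the rectal figure can be: 60 mL × 1.47E+09 per mL = 8.82E+10. A per-mL emulsion count would also not describe a freeze-dried fill, if that is what is supplied.

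The Statistical analysis, Sample size, Specialized analyses and Endpoints sections contain no analysis or endpoint that uses CFU.

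**The case against.** The strongest reply is that the criterion may be correct on its own terms. It is worded for the FMT capsules, and the listed ingredients may be exactly those of the active product. If trehalose is also in the active capsule, the general words before the parenthesis could already cover it even though the list omits it. That stands. It leaves only a placebo-only excipient clearly outside the rule; on the text as written, carboxymethylcellulose is the one named solely for placebo.

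Second, composition and fill volume may be in the cross-referenced Drug Master File and IND, which are not part of the protocol. That is also fair, and is why the remedy is reconciliation and not a corrected list. It does not help site staff who screen from the protocol.

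Three stronger readings are tempting, and the documents do not support them:

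- **The allergy list belongs to an emulsion capsule left over from the earlier supplier.** Nothing ties the list to an emulsion. The change of supplier makes carried-over text plausible but does not show it.
- **The active capsule is freeze-dried, so all 100 patients would swallow trehalose.** Freeze-drying is mentioned only in explaining what trehalose is for. The storage and thawing instructions do not settle the formulation.
- **Results could not be linked to a dose.** The oral dose is defined as five capsules, and dose and lot number are recorded for every treatment. What cannot be derived from the protocol is the CFU content.

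**Conclusion.** The point holds in a limited form. Exclusion (5) does not match the oral placebo that the protocol describes: 0 of its 2 fill ingredients are listed, the wording covers only the active capsules, and no other criterion names them. A patient with a known allergy to a placebo-only excipient can pass the screen as written and has a planned 50-in-100 chance of being assigned that placebo.

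This rests on the placebo description being accurate for the capsules actually supplied. The documents give no frequency for such allergies, so the number of patients affected is unknown and may be small; 50 counts planned exposure and does not measure harm.

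Whether the active capsule is an emulsion or freeze-dried is not stated, so the product behind the quoted counts is unclear. That is a documentation gap. No sample size, power or analysis result changes.

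**What to change.** Reconcile four places with the product file: the concentration tables, the placebo description, Safety-related exclusion (5), and the capsule section of Preparation and handling. After that:

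- the allergy exclusion should match the ingredients of both the active and the placebo capsules as supplied;
- the concentration statement should name that same product, with the fill volume if a CFU content is to be reported.

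The sponsor must supply the composition; it cannot be inferred from the protocol. The cost is protocol wording and one screening question. The design, sample size and analyses are unaffected.

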Ruminococcaceae. In our published experience, a single enema from a rationallyderived donor was associated with significantly lower total and HE-related hospitalizations compared to patients who were randomized to standard of care, with a stable long-term course over >1 year¹⁰. Our data show that FMT was associated with favorable changes in fecal bile acid (BA) profile with a decrease in proportions of fecal secondary BAs, conjugated BAs and increase in sulfated BAs, indicating a healthier milieu. We also have preliminary data defining the safety of oral FMT capsules in patients with cirrhosis and HE in a current trial led by us¹¹. The use of combined oral *and rectal routes of FMT, which can potentially alleviate both small bowel and colonic translocation are likely to be better than either alone*.

Details of the team's experience with FMT in cirrhosis using enema¹⁰:

In the trial conducted by us under IND 16452, we have recruited 20 subjects with cirrhosis and recurrent HE (the same population proposed for this trial). All subjects completed the 5-month follow-up without SAEs that were associated with FMT. The baseline subject characteristics are:

	No-FMT group	FMT group	P value
	(n=10)	(n=10)	
Age	62.9±9.8	64.5±5.1	0.65
Gender (Men/Women)	10/0	10/0	1.0
Race (Caucasian, African- American, Hispanic, others)	6/3/1/0	7/2/1/0	0.9
MELD score	13.2±3.7	12.0±2.9	0.36

None of the subjects reached a grade of 3 or change in >2 of any of their GI symptoms throughout the study. Similarly, none of the subjects developed clinically relevant hepatic encephalopathy or significant changes in liver chemistries or labs (WBC

>12,000 or <1000/ml, MELD >8 increase, AST/ALT/ALK>10 times ULN). As shown in the table below, there was a significant improvement (reduction in the MELD score) in the FMT group compared to the no-FMT group at day 1 post-FMT (day 6) and day 30 post-FMT (day 35) compared to baseline. No changes in the WBC count were observed.

	No-FMT group	FMT group	P value
	(n=10)	(n=10)	
MELD score			
Day 0 minus day 6	0.6±1.4	-1.5±1.4	0.004
Day 0 minus day 12	0.4±1.3	-0.2±1.3	0.3
Day 0 minus day 35	1.2±2.4	-0.9±1.7	0.04
Serum WBC count			
Day 0 minus day 6	-0.1±0.6	0.1±1.2	0.60
Day 0 minus day 12	-0.53±0.9	0.2±1.0	0.10
Day 0 minus day 35	0.22±0.5	0.2±0.9	0.95

There was a significant reduction in hospitalizations and improvement in brain function in patients randomized to FMT+ antibiotics compared to those randomized to SOC¹⁰.

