Group 1: Oral and enema FMT, Group 2: Oral FMT+ enema placebo, Group 3: Oral placebo + enema FMT, Group 4: Both placebo *Visit 2* After re-confirming eligibility, the patient will be seen within 3±5 days of visit 1. Vital signs and weight will be measured. Targeted physical exam will be done based on any symptoms.

Their symptom diaries and dietary recall will be examined. Stool, blood and urine will be collected and processed (see section below), including urine

pregnancy testing for women of child-bearing potential. After this we will administer the assigned intervention by enema and oral capsules. This has been tolerated without any issues in our current protocols. These will be dispensed from our VAMC Investigational Pharmacy, which has been handling these for our prior and current FMT trials. The

following will be recorded in all FMTs (dose, Unit ID/Lot# of each treatment, Expiration Date and storage condition) The patient will be observed for a further 1 hour and then given another stool kit to bring back 10±5 days from this visit (Visit 3). All subjects will be given contact information for the study team to call in case any issues arise.

Optionally, subjects may elect to combine Visits 1 and 2 to minimize potential COVID exposure. In this case, stool collection kit would be mailed to subject before visit, and the staff would provide further instructions to subject on their use. The subject may determine whether he/she will collect a stool sample to bring to the study clinic visit. In the event the subject decides not to participate in the study, the stool collection kit would be discarded.

Visit 3: We will see the patient in the McGuire VAMC at day 15, at which point, dietary recall will again be performed along with changes in GI or other adverse events using interview and review of the symptom diaries. If no adverse event (AE) or serious adverse events (SAE) occur (standard definitions and in the human subjects protection section per FDA specifications), the subject will continue in the study. Vital signs and weight will be measured. Targeted physical exam will be done based on any symptoms. The stool sample, blood and urine will be collected for microbiota and safety analysis. Changes in blood counts that prompt attention (MELD score increase by 8, WBC count change to >13,000 or <2,000) will be monitored. If all is well, then subjects will be discharged with another stool kit and instructions for the last visit 15±3 days later (visit 4).

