Specific safety findings will result in temporarily suspending enrollment until a safety review is convened, the objective of which is to determine whether the study should continue per protocol, proceed with caution, be further investigated, be discontinued, or be modified and then proceed. Suspension of enrollment is another potential outcome of a safety review. This will be done if the assigned infection is in the FMT group since this patient population is prone to infections.

Subsequent review of serious, unexpected, and related AEs by the Data and Safety Monitoring Board, IRB, the PI, or the FDA or relevant local regulatory authorities may also result in suspension of further trial interventions/administration of FMT at a site. The FDA and PI retain the authority to suspend additional enrollment and study interventions/administration of FMT for the entire study, as applicable. The PI and the adjudication panel will make the initial decision. The subsequent safety review by the IRB and FDA will then decide if the study can resume.

Findings that will trigger a safety review are

Findings that will trigger a safety review are

- o Death related to FMT material or study procedures in any subject;
- New potentially transmitted infection in five or more subjects assigned to FMT - i.e., cannot exdude transmission and/or attribution is

pending investigation/Data Monitoring Committee (DMC) adjudication;

- Any single potential transmitted infection assessed as possibly, probably, or definitely related to FMT by the investigator and DMC.
- One or more subjects assigned to FMT has a serious, unexpected AE assessed as possibly, probably, or definitely related to FMT by the investigator and DMC; Five or more subjects (per assigned group) develop a new diagnosis of a medical condition or immune-mediated disease considered probably, or definitely related to FMT.
- Five or more severe AEs of a similar nature occurring in different subjects and assessed as definite, possible or probable relatedness to study product in groups assigned to FMT (per assigned group)

FDA/CBER will be notified by phone or fax within 72 hours if the study is halted for review.

Individual study halting rules

- (1) patient's choice
- (2) change in GI adverse events with a magnitude of 3 increase over baseline
- (3) fever and signs of infection (including WBC count >12,000/ml)
- (4) SAE development including cirrhosis complications (OHE) and hospitalizations for

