- any cause including bleeding, nausea, vomiting, or other GI conditions
- (5) increase in MELD score by 8 or more
- (6) Increase in AST, ALT or Alkaline phosphatase to 10X ULN
- (7) Non-elective Hospitalization

Even if the subject is withdrawn before 30 days, they will still be followed till 6 months for safety.

Health risks (please see adverse events table attached):

Adverse events will be both for the FMT material, placebo as well as for the procedures. These risks are listed in the Risk Section of the informed consent.

These possible adverse events will be:

- (a) Fever: yes or no answer with grading based on actual temperature on examination
- (b) diarrhea (will be asked to grade them from 0-4 compared to baseline)
- (c) abdominal cramping and pain (will be asked to grade them from 0-4 compared to baseline)
- (d) vomiting (will be asked to grade them from 0-4 compared to baseline)
- (e) Development of HE (Altered mental status) in every group: will be monitored by clinical examination through the West-Haven Criteria²⁵. We will be closely monitoring all subjects for this development, including a clinical examination by a gastroenterologist at every visit.

(f) Development of infections specifically spontaneous bacterial peritonitis -Fever will be reconfirmed by measuring by the study nurse and if it is confirmed, a detailed investigation into the cause of the fever will be performed as part of standard clinical care and the patient will be withdrawn from the study.

-Vomiting, constipation, GI bleeding, abdominal cramps and diarrhea: If the patient's diarrhea and abdominal cramps change in a magnitude of 3 over their baseline values per the AE chart (patients with cirrhosis often have these symptoms at baseline), they will be withdrawn from the study.

-Infections that occur in the FMT group will be thoroughly investigated according to standard clinical care to prove whether they were associated with the FMT.

Adverse Event Grading Chart

 Volunteer Study ID:
 Date:
 Time:

 Study Start Date:
 Current Visit number:

*Volunteer's responses will be marked on grading sheet by circling the appropriate grade or indicating no symptoms.

PARAMETER COMPARED TO BASELINE	GRADE 1 MILD	GRADE 2 MODERATE	GRADE 3 SEVERE	GRADE 4 POTENTIALLY LIFE-THREATENING
ESTIMATING SEVERITY	(GRADE		•	•

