Dehydration	Increased oral fluids indicated; dry mucous membranes; diminished skin turgor	IV fluids indicated <24 hours	IV fluids indicated >24 hours	Life-threatening consequences (e.g. hemodynamic collapse)
Constipation	NA	Persistent constipation requiring regular use of dietary modifications, laxatives, or enemas	Obstipation with manual evacuation indicated	Life-threatening consequences (e.g., obstruction)
Procedural Enema	Rectal discomfort; minor bleeding <24 hours on toilet paper	Rectal discomfort; minor bleeding >24 hours on toilet paper	Gross hematochezia	Bowel perforation
Change in mental status (West-Haven Criteria)	No change in orientation and no asterixis	Disorientation to time, asterixis	Disorientation to place or person, asterixis, lethargy and stupor	Coma
MELD score increase (includes INR, bilirubin and creatinine)	<3	3-7	>8	NA
Serum WBC	NA	NA	>12,000/ml or <1000/ml	NA
AST	NA	≥ 5.0 to < 10.0 x ULN	≥ 10.0 x ULN	NA
ALT	NA	≥ 5.0 to < 10.0 x ULN	≥ 10.0 x ULN	NA
Alkaline phosphatase	NA	≥ 5.0 to < 10.0 x ULN	≥ 10.0 x ULN	NA

Specific investigation of the infection related to the FMT in those assigned to the FMT group:

- 1. Regular clinical care of the subject according to the infection developed will include the appropriate cultures and relevant antibiotics will be started
- 2. Stool tests from the patient will be compared to the donor safety sample when a CLIA-

certified assay is available

3. Contact will be made with the FMT suppliers to evaluate this batch of the donor. Specifically, the cross-referenced drug master file has the means to track down the lots and batches of the donors. In the event of a suspected adverse event related to the potential transmission of an infection, an immediate initial consultation will be held between the researchers and the Chief Medical Officer of Molecular and Cellular Therapeutics (GMP) facility at the University of Minnesota ([name]) to gather further information. This will be followed by a detailed collaborative investigation as follows:

The investigation will entail:

a. Strict donor material quarantining during the investigation

b. Rescreening of the donor safety aliquot and the donor for infectious diseases as well as risk factors for the suspected infectious disease

c. Consultation with external experts in infectious diseases and gastroenterology with extensive experience in FMT.

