d. Full Advisory board review at Molecular and Cellular Therapeutics (GMP) facility at the University of Minnesota to track the donors

Laboratory:

Lab values for WBC counts, serum AST, ALT, Alkaline phosphatase, serum bilirubin, INR and serum creatinine (all three are in MELD score) will be followed.

These criteria will be graded per the chart as well.

The lab values that will be followed from an adverse event perspective will be:

- WBC count: a new >12,000/ml or <1000/ml in the presence of fever will necessitate investigation of an infectious source
- Worsening of the MELD score by 8 or higher will be considered significant
- Increase in AST, ALT and alkaline phosphatase >10 ULN will be considered significant although this change is not expected in cirrhotic subjects

[name] asks subjects to allow him to keep a portion of their blood, urine and stool specimens collected during the study to be used for future testing. Subjects agreeing to this will have a portion of their blood, urine and stool specimens stored in a research laboratory at the McGuire DVAMC. The samples will be de-identified. This means that no information that can identify a subject will appear on the samples. Subjects do not have to agree to this in order to participate in the study. If at any time during or after the study, a subject decides they want their samples destroyed, the subject can contact [name] at [contact] and request that their samples be destroyed.

Adverse Events Reporting

[name] will function as both the Investigator and the Sponsor during the conduct of this study. [name] will be responsible for reporting all safety observations (adverse events and serious adverse events) to the FDA

A. Definitions

1. Adverse Event (AE)

An AE is any untoward medical occurrence in a patient or study subject administered FMT due to the material or procedure that does not necessarily have a causal relationship with this treatment. An AE can therefore be any unfavorable and unintended sign (including an abnormal laboratory finding), symptom, or disease temporally associated with the use of a FMT, whether or not related to the FMT.

• AEs may be new events or may be pre-existing conditions that have become aggravated or have worsened in severity or frequency.

• AEs may be clinically significant changes from baseline in physical examination, laboratory tests, or other diagnostic investigation (e.g. laboratory results, radiographic findings).

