All AEs, regardless of seriousness, severity, or causal relationship to FMT, will be recorded in the AE section of the subject case report form.

2. Reporting of FMT Exposure during Pregnancy

If a female subject becomes pregnant during the course of study, the Investigator/Sponsor is required to follow up on the pregnancy until it has completed. The outcome of the pregnancy and the status of the newborn (if applicable) will be reported to the local IRB within 24 hours of becoming aware.

3. Reporting of Safety Observations by the Investigator/Sponsor

Any occurrence of the following events or outcomes must be reported expeditiously by the Investigator/Sponsor to the local IRB (within 5 days of becoming aware) and will be responsible for reporting the event to the FDA:

- 1. SAE *related* to FMT material
- 2. Death of a subject *related* to FMT material

The site Investigator/Sponsor is to report any safety observations from the list above to the FDA within **72 hours** of becoming aware of the event. Any observation that is also an AE will be recorded on the subject's case report form along with any actions taken. If not all information is available at the time of initial report, follow up SAE reports will be completed and submitted.

Any occurrence of the following events or outcomes must be reported by the Investigator/Sponsor to the local IRB and for reporting the event to the FDA:

- 1. SAE *unrelated* to FMT material
- 2. Death of subject unrelated to FMT material
- 3. New or worsening medical condition, or new medications

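### The upper WBC alert at Visit 3 is looser than the chart's Grade 3 limit, and a MELD rise of exactly 8 has no chart grade

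*Combined protocol and SAP*

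**What the plan says.** **WBC.** The Visit 3 description, under Procedures, sets the alert: "Changes in blood counts that prompt attention (MELD score increase by 8, WBC count change to >13,000 or <2,000) will be monitored". In the Adverse Event Grading Chart, the Serum WBC row has one populated cell, Grade 3: ">12,000/ml or <1000/ml". Grades 1, 2 and 4 are marked not applicable. Item 3 of the Individual study halting rules reads "fever and signs of infection (including WBC count >12,000/ml". The Laboratory section says that "a new >12,000/ml or <1000/ml in the presence of fever will necessitate investigation" of an infectious source.

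**MELD.** The chart row "MELD score increase (includes INR, bilirubin and creatinine") gives <3 as Grade 1, 3-7 as Grade 2 and >8 as Grade 3, with no Grade 4. Item 5 of the Individual study halting rules is "increase in MELD score by 8 or more". The Laboratory section treats a worsening of 8 or higher as significant.

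**Link to grading.** The Laboratory section sends these values to the chart for grading. Assessment of Adverse Events, item 1, also ties severity to the adverse event table.

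**The concern.** An alert limit should trip at or before the value that the grading chart calls severe. On the upper WBC side it trips after. Visit 3 is the scheduled laboratory check between the first dose and the second oral dose at Visit 4, so staff who work from its list could pass over a count that the chart puts at Grade 3.

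For MELD, the chart is silent at the value where the other rules start to act. Severity also feeds a study-level rule. Under Overall Study Halting Rules, a safety review follows five or more similar severe events in different subjects within an assigned FMT group, if they are judged at least possibly related. With 25 patients per group, that is 5/25 = 20% of a group. Whether a MELD rise of 8 counts towards the five should not depend on who grades it.

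**Working it through.** No power or alpha figure is involved. The check sets the limits side by side and applies them as written. The Visit 3 WBC limits carry no unit and are read in the chart's unit. MELD is taken as a whole number unless stated otherwise.

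**Step 1: limits by section**

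| Section | WBC, upper | WBC, lower | MELD rise |
|---|---|---|---|
| Visit 3 | >13,000 | <2,000 | 8 |
| Adverse Event Grading Chart, Grade 3 | >12,000 | <1,000 | >8 |
| Individual study halting rules | >12,000, with fever and signs of infection | none | ≥8 |
| Laboratory | >12,000, with fever | <1,000, with fever | ≥8 |

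The account of the earlier enema trial uses ">12,000 or <1000/ml, MELD >8 increase". That is background and does not govern this trial.

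**Step 2: WBC, upper side.** The gap is 13,000 − 12,000 = 1,000. Take a count of 12,500 without fever or signs of infection:
- Chart: 12,500 > 12,000, so Grade 3.
- Visit 3: 12,500 is not above 13,000, so no alert.
- Halting and Laboratory rules: not met, because both are tied to fever.

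**Step 3: WBC, lower side.** Counts from 1,000 to below 2,000 raise the Visit 3 alert but have no chart grade. Here the alert is tighter than the grade, as an early alert should be. Only the upper limit runs the wrong way.

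**Step 4: MELD**

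| Rise | Chart grade | Individual halt (≥8) | Laboratory significance (≥8) |
|---|---|---|---|
| 7 | 2 | no | no |
| 8 | none | yes | yes |
| 9 | 3 | yes | yes |

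If MELD were kept unrounded, the ungraded interval would be above 7 up to and including 8.

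**Step 5: could the chart's >8 be a ≥8 damaged in file conversion?** This is unlikely. The same chart prints ≥ correctly in the AST, ALT and alkaline phosphatase rows, and the enema-trial account also writes >8.

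**Step 6: after the edits.** With >12,000 at Visit 3, the count of 12,500 raises the alert. With ≥8 in the chart, a rise of 8 becomes Grade 3, and every whole-number rise has a grade that agrees with the halting and Laboratory rules.

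**The case against.** The strongest reply is that an alert list and a severity chart do different jobs. A count of 12,500 without fever can satisfy every rule at once: Grade 3, recorded, no work-up, no halt. Nothing says that staff may ignore values outside the Visit 3 list. Visit 3 itself includes a review of adverse events, the Laboratory section has WBC followed and graded at no particular visit, and the reporting section states that "All AEs, regardless of seriousness, severity, or causal relationship to FMT, will be recorded in the AE section" of the case report form. For MELD, the three rules that prompt action agree at 8, so only a grading label is missing. Assessment of Adverse Events also offers a general severity scale. Finally, the proposed edits leave the lower WBC limits different, so differing limits cannot be an error in themselves.

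Much of this stands, and it is why the point is minor. The value should still be graded and recorded, a febrile patient is covered, the individual MELD halt works, and no documented case shows the gap changing a study-level decision.

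It does not remove the point. An alert set beyond the severe grade gives no early warning, whereas the stricter lower limit does, so the two mismatches are not alike. The general scale is worded by limits on routine activity, which a laboratory-only change need not cause, so it is a poor substitute for the missing MELD grade.

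**Conclusion.** The concern holds on both parts, as a minor inconsistency. The affected values are an isolated WBC of 12,001 to 13,000 at Visit 3 and a MELD rise of exactly 8 at any visit. The documents do not say how many patients this would involve; few are likely, and no frequency is claimed.

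For this trial, 13,000 is the one upper WBC limit that departs from 12,000, and the chart's >8 is the one MELD limit that leaves out 8. The conclusion assumes whole-number MELD and a common WBC unit. What is affected is the consistency of safety monitoring and event grading. Sample size, alpha, the primary endpoint and the individual halt at a MELD rise of 8 are not affected.

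**What to change.** Make two edits:

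1. Visit 3: change the upper WBC limit from >13,000 to >12,000. The lower limit of <2,000 may stay as an early alert.
2. Adverse Event Grading Chart, MELD row: change Grade 3 from >8 to ≥8.

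If sites keep MELD unrounded, values between 7 and 8 would still have no grade; a note that MELD is rounded to a whole number would close that gap.

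The cost is wording only. No visit, sample size or analysis changes.
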